4.2.2.1 Implementation of Strategies for Intercurrent Event Handling and Data Point Selection

Prior to performing the MMRM model, missing data will be handled in alignment with the estimand strategy for ICEs (described in Section 1.1).

The hypothetical strategy will be used to handle all of the ICEs in the primary estimand. This strategy would estimate the full efficacy potential of elinzanetant in the ideal situation if participants adhered to randomized study treatment up to week 4 without taking prohibited concomitant medications impacting sleep.

Any data that occur after premature discontinuation of study treatment will be discarded. For temporary treatment interruption and intake of prohibited concomitant medication, only data during the timeframe of the ICE will be discarded. For example, if a participant had a temporary treatment interruption at week 4 but not at week 12, only data at week 4 will be discarded while week 12 data will be utilized in the analyses. For prohibited concomitant medications, data collected during the concomitant medication period and within the washout period for that medication will be discarded. Since PSG assessments will be performed on 2 consecutive nights at each visit, only nights that are performed after premature discontinuation of study treatment or fall within the ICE timeframe will be discarded (e.g., if study treatment was taken on night 1 but not on night 2 then night 1 will be included and night 2 discarded). Details regarding how the ICEs are defined and will be identified are described in Section 6.4.

Given that all unobservable data (i.e., data discarded or missing during an ICE or missing values outside of the time frame of any ICE) will be modeled under the hypothetical scenario "if participant complied with treatment" (i.e., having no premature treatment discontinuation, no treatment interruption in the respective week and no intake of prohibited concomitant medications), it can be assumed that the missing or discarded data have a similar distribution as the observed data of participants who comply with treatment, given the covariates included

Version 2.0 Page: 22 of 57

in the model (missing at random (MAR) mechanism). Therefore, missing or discarded data will be handled implicitly through using the MMRM model as specified in Section 4.2.2.

The MMRM model will exclude participants who have no post-baseline assessment from the analysis. Hence, if more than 5% of participants in the analysis set (FAS) have no post-baseline data (i.e., excluded from the MMRM model), Monte Carlo Markov Chain (MCMC) MI will be used to impute missing or discarded values prior to performing the MMRM model using the SAS code below.

```
PROC MI DATA=data OUT=outmi seed=22423 nimpute=500;

MCMC CHAIN=multiple IMPUTE=full INITIAL=em;

VAR change_wk4 change_wk12 baseline treatment average_HF1 average_HF2;
RUN;
```

Where average_HF1 and average_HF2 are indicator variables representing the level <35 moderate to severe HFs per week and ≥35–<50 moderate to severe HFs per week respectively of the variable actual stratification factor.

Each imputed dataset will be analyzed using the MMRM model specified in Table 4-2 to obtain an estimate of the treatment effect. The results will be combined using Rubin's rule (Rubin 1987) to obtain an overall mean change from baseline and overall estimated treatment effect. A total of 500 MI steps will be used.

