4.1 General Considerations

The statistical evaluation will be performed by using the software SAS (release 9.4 or higher; SAS Institute Inc., Cary, NC, USA) and/or R (version 3.5.2 or higher; R Foundation for Statistical Computing, Vienna, Austria).

All variables will be summarized using descriptive statistics as appropriate by study treatment. Continuous variables will be summarized using at least the following descriptive statistics: number of non-missing observations and missing data, arithmetic mean, std dev, median, minimum, and maximum. The geometric mean, geometric std dev and CV will be provided instead of the arithmetic mean and std dev for variables where lognormal distributions are assumed. Categorical data will be summarized with frequency tables with the number of observations and percentages. Confidence intervals (CI) will be 2 sided with a confidence level of 95% for descriptive statistics and 90% level from the MMRM. Treatment differences will be provided for elinzanetant vs placebo.

Variables recorded in the electronic case report form (eCRF) and relevant derived variables will be shown in data listings, whereby only randomized participants will be included. Data from screening failures will only be shown in the 'Screening failure' listing.

Number of decimal places for summary statistics will be the following:

Table 4-1: Number of Decimal Places for Summary Statistics

Statistic	Number of decimal places
Minimum, maximum	Same as original data
Mean, median, std dev	1 more than in original data
Frequencies (%)	1 digit

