	If convergence cannot be attained with the unstructured correlation matrix, the following alternative structures will be attempted in the specified order: autoregressive(1) (AR(1)), and compound symmetry (CS). The first structure in this list with which the model converges will be used. If AR(1) structure is used, a random subject intercept will also be included in the model. If multiple imputation (MI) is performed, then this will need to be applied for each imputed dataset (see Section 4.2.2.1).	
Equation		
1	$Y_{ijkl} = \mu + \beta x_i + t_k + r_l + v_j + (tv)_{jk} + s_i + \varepsilon_{ijkl}$	
	where Y_{ijkl} is the change from baseline in WASO to week j for subject i (with treatment	
	k and baseline average weekly frequency of HFs l),	
	μ is the intercept,	
	β is the baseline covariate effect (baseline coefficient), x_i is the baseline WASO for subject i ,	
	t_{L} is the fixed effect of treatment k ($k=Elinzanetant$, $placebo$),	
	r_{l} is the fixed effect of average weekly frequency of HFs l	
	$(l=<35 \text{ moderate to severe HFs per week}, \ge 35-<50 \text{ moderate to severe HFs per week}, \ge 50 \text{ moderate to severe HFs per week}, v_i \text{ is the fixed effect of week } j (j=4, 12),$	
	$(tv)_{jk}$ is the interaction effect of treatment k by week j,	
	$s \sim \text{Normal } (0, \sigma_s^2) \text{ is the random effect of subject } i \text{ (only if } AR(1) \text{ covariance structure}$	
	is used),	
	$\varepsilon_{ijkl} \sim \text{Normal } (0, \sigma^2)$ represents the residual variance component with	
	$\operatorname{corr}\left(\varepsilon_{ij},\varepsilon_{ij}\right)=\rho_{jj},j\neq j'.$	

Version 2.0 Page: 21 of 57

SAS code:	PROC MIXED data=DATA method=ML;
	CLASS subject treatment average_HF week; MODEL change = baseline treatment average_HF week treatment*week /ddfm=KR outp=resid s; REPEATED week / subject=subject type=un; RANDOM subject; /*only if AR(1) covariance structure is used*/
	LSMEANS treatment*week /alpha=0.1 cl diff obsmargins; ESTIMATE 'Elinzanetant - Placebo at Week 4' treatment 1 -1 treatment*week 1 0 -1 0 /alpha=0.1 cl; ESTIMATE 'Elinzanetant - Placebo at Week 12' treatment 1 - 1 treatment*week 0 1 0 -1 /alpha=0.1 cl; ODS OUTPUT TESTS3=TYPE3 eff LSMeans=LSMEAN ESTIMATES=EST;
	RUN;

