Although all participants are expected to be followed after ICEs temporary study treatment interruption and intake of prohibited concomitant medication, some missing data may occur. Missing values that occur while the participants continue on their randomized treatment are assumed MAR. Such missing values could be intermittent or monotone and will be imputed using a MCMC MI method.

The washout method (Wang et al. 2003) will be used to impute the unobservable data under the hypothetical scenario for the ICE premature discontinuation of study treatment. A placebo-effect is expected to be seen with the placebo group while the elinzanetant treatment effect will consist of both the placebo-effect and the effect of elinzanetant. The washout method effectively 'washes out' any pre-ICE treatment effect of elinzanetant in participants with an ICE randomized to elinzanetant, while modeling the mean placebo-effect. Missing data in participants randomized to placebo will be assumed MAR.

For participants randomized to elinzanetant, the imputation model will have the dependent variable as the endpoint measurement at week 4 with the baseline measurement and the stratification factor average weekly frequency of moderate-to-severe HFs as independent variables. The imputation model will be estimated only based on placebo participants who

Version 2.0 Page: 24 of 57

remain in the study through week 4 and have available data at week 4. Similarly, week 12 values missing after an ICE will be imputed using the same model specification but with endpoint measurement at week 12 as the dependent variable.

The imputation will be done using a regression model (PROC MI with MONOTONE REG) including covariates described above for each time point and using the MNAR statement to estimate the model from placebo participants only.

To impute missing data for participants randomized to placebo, using MAR assumptions, the imputation will be done using a regression model including measurements from all timepoints before the timepoint being imputed in addition to baseline measurement and the stratification factor (PROC MI with MONOTONE REG). All placebo participants will be included in the imputation model.

PROC MI will be run with the random seed setting SEED=22423 to produce 500 imputed datasets.

Similar analysis steps (i.e., imputation, modeling and combining results) as detailed in Section 4.2.2 will be applied.

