There are no data available on the primary endpoint WASO measured by PSG in women with sleep disturbance associated with the menopause. Therefore, the standard deviation used in the sample size calculation is obtained from a study in patients with insomnia disorder (Mignot et al. 2022). Assuming the pooled standard deviation is 33.2 for the change from baseline in WASO at week 4, a total sample size of 70 participants (35 per arm) would give a 90% probability that the 2-sided 90% confidence interval will have a half width of 14.7 minutes or less.

To account for missing data and possible inflation in variability due to missing data imputation, a total of approximately 78 (39 per treatment) will be randomized in a 1:1 ratio to both treatments. Approximately 223 participants will be screened to achieve 78 randomized participants.

Version 2.0 Page: 43 of 57

6. Supporting Documentation

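### If multiple imputation is triggered in the main analysis, pooling by the cited 1987 rule discards the small-sample degrees of freedom and makes the 90% CI about 1.3–2.1% too narrow

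*SAP*

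**What the plan says.** The SAP plans no hypothesis test; the primary result is an estimated difference with an interval. Section 4.1 sets the level: "confidence level of 95% for descriptive statistics and 90% level from the MMRM".

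The SAS code in Table 4-2 requests Kenward-Roger degrees of freedom through "ddfm=KR outp=resid s", and estimates the model by maximum likelihood.

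In Section 4.2.2.1 missing values are by default left to the MMRM. The exception is "if more than 5% of participants in the analysis set (FAS) have no post-baseline data", which the SAP equates with being left out of the model. All missing or discarded values are then imputed 500 times, the same MMRM is fitted to each dataset, and "The results will be combined using Rubin's rule". A 1987 text is cited for the rule. The SAP prints code for the imputation and for the model, but none for the pooling step. It gives neither a complete-data degrees of freedom nor a small-sample correction.

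The first supplementary analysis (Section 4.2.3.1) also relies on imputation ("PROC MI will be run with the random seed setting SEED=22423 to produce 500 imputed datasets") and refers back for the combining step.

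**The concern.** The 1987 degrees of freedom treat the complete-data analysis as if it had infinitely many. That does little harm in a large trial. With 78 women and 500 imputations, it replaces a t quantile on 60-odd degrees of freedom by what is in effect a normal quantile.

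The interval multiplier would then shrink simply because the analysis passed through imputation, although imputation was needed only because data were missing. The direct MMRM and the sample-size calculation both use small-sample quantiles; only this branch drops them. What is at stake is the nominal level and the comparability of the interval for the primary treatment difference. The point estimate and the sample size are unaffected.

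**Working it through.** **Inputs from the documents.** 90% two-sided CI (SAP 4.1). Standard deviation 33.2 minutes: "Assuming the pooled standard deviation is 33.2 for the change from baseline in WASO at week 4" (SAP Section 5). 35 evaluable per arm and 78 randomized (SAP Section 5). m = 500 imputations (SAP 4.2.2.1). Trigger: 5% of 78 = 3.9, so 4 or more women.

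**Inputs that are assumptions.** Neither of these is in the documents:
- Complete-data degrees of freedom ν_com: 72 as the central value (78 less about six mean parameters), range 64–76.
- Fraction of missing information γ: 0.10 as the central value, range 0.05–0.30.

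**Step 1: reproduce the plan's figure.** The plan says 35 per arm "would give a 90% probability that the 2-sided 90% confidence interval will have a half width of 14.7 minutes or less".
- SE = 33.2 × √(2/35) = 7.94 minutes.
- Half-width reached with 90% probability = t(0.95, 68) × SE × √(χ²(0.90, 68)/68) = 14.65 minutes, which agrees with 14.7.
- With a normal quantile in place of t the result is 14.45, so the stated figure fits the t calculation better.

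**Step 2: degrees of freedom under each pooling rule.**
- 1987 rule: ν = (m − 1)/γ². At γ = 0.10 this is 499/0.01 = 49,900.
- Barnard-Rubin: ν_obs = [(ν_com + 1)/(ν_com + 3)] × ν_com × (1 − γ) and ν_BR = 1/(1/ν + 1/ν_obs). With ν_com = 72 and γ = 0.10, ν_obs = (73/75) × 72 × 0.90 = 63.1 and ν_BR = 63.0.

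**Step 3: effect on the interval**, at the planning SE of 7.94 minutes.

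| ν_com | γ | 1987 df | Barnard-Rubin df | t(0.95), 1987 | t(0.95), B-R | Too narrow by | Minutes | Approx. coverage |
|---|---|---|---|---|---|---|---|---|
| 76 | 0.05 | 199,600 | 70.3 | 1.6449 | 1.6668 | 1.32% | 0.17 | 0.8955 |
| 72 | 0.10 | 49,900 | 63.0 | 1.6449 | 1.6694 | 1.47% | 0.19 | 0.8950 |
| 64 | 0.30 | 5,544 | 43.1 | 1.6451 | 1.6810 | 2.13% | 0.28 | 0.8928 |

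In the central case the half-width is 13.05 minutes under the 1987 rule and 13.25 under Barnard-Rubin. The direction is the same throughout the grid.

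**Step 4: simulation check.** Setting: 78 participants, Week 4 analysis of covariance, proper imputation under missing at random, 100 imputations, 6,000 runs, unbiased residual variance. The Monte Carlo standard error is √(0.9 × 0.1/6,000), about 0.4 percentage points, but both rules were applied to the same datasets.

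| Missing | Coverage, 1987 df | Coverage, small-sample df |
|---|---|---|
| 6% | 89.4% | 89.9% |
| 10% | 89.3% | 90.0% |
| 20% | 88.6% | 89.1% |

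A second simulation under missing at random gave 89.6% against 90.0–90.1%. The gap of about half a point agrees with the formula.

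**The case against.** **The SAP does not print the pooled degrees of freedom.** This stands. The large-sample form is inferred from the 1987 citation and the absence of any adjustment. A reader might infer that the sponsor deliberately chose it; the documents do not show that. Following the citation as written still leads there, and one sentence would settle it.

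**The branch may never run.** This also stands. A reader might infer that the trigger is close to certain, because 78 are randomized to obtain 70 evaluable. But those 8 are not 8 women without post-baseline PSG. The margin also covers variance inflation from imputation, evaluability refers to the Week 4 analysis, and a woman with only Week 12 data stays in the MMRM.

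**The shared pooling step might suggest the same defect in Section 4.2.3.1.** It does not follow. There, women who discontinue elinzanetant are imputed from a placebo-only model, and Rubin's variance tends to overstate the sampling variance. In one simplified simulation (39 per arm, 2, 4, 6 or 8 discontinuers per arm assumed) coverage with the 1987 degrees of freedom was 91.3%, 92.9%, 94.4% and 96.2%. Another gave 90.4% and 92.8% at 2 and 4 per arm. On-treatment values imputed under missing at random would dilute this, but smaller degrees of freedom would only widen an interval that already tends to be conservative.

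**The correction may not restore 90%.** Correct. Table 4-2 uses maximum likelihood. With ML residual variance, the missing-at-random simulation gave 88.3–88.4% under the 1987 rule and 88.8–89.0% after the correction, at 6–10% missing. That simulation omitted the Kenward-Roger covariance adjustment, so it shows a separate source of narrowing and does not measure the specified model's coverage.

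**The size is immaterial.** Largely fair: 0.2 minutes is 12 seconds, under half of one 30-second PSG epoch (SAP Table 6-2 equates 20 epochs with 10 minutes). No test or decision threshold depends on it.

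**Conclusion.** The point holds for the conditional imputation branch of the main analysis in SAP 4.2.2.1, and only there. If 4 or more of the 78 women have no post-baseline PSG at all, pooling as cited gives degrees of freedom of about 5,500 to 200,000 where about 43 to 70 are appropriate. The Kenward-Roger request in Table 4-2 then has no influence on the pooled interval.

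The 90% CI is about 1.3–2.1% too narrow (0.17 to 0.28 minutes), with coverage of about 89.3–89.6%. This rests on assumed complete-data degrees of freedom of 64–76, assumed missing information of 5–30%, an SE at its planning value, and an unbiased residual variance. The last assumption is not secured by the ML estimation in Table 4-2, so these figures isolate the effect of the degrees of freedom.

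This is a minor technical correction. It does not support a claim of under-coverage in the first supplementary analysis.

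**What to change.** In SAP 4.2.2.1, state that the imputed-data results are pooled with Barnard-Rubin small-sample degrees of freedom. In PROC MIANALYZE, set EDF= to the Kenward-Roger degrees of freedom of the Week 4 contrast, and separately to that of the Week 12 contrast. Because each of the 500 fits yields its own value, also say which one is supplied, for example the mean across imputations.

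Make no corresponding change in 4.2.3.1 on these grounds. The ML estimation in Table 4-2 is a separate matter that this change does not address.

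The cost is one sentence and one SAS option, with no new data. The downside is a slightly wider interval, by about 0.2 minutes each side at the planning values.

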4.2.3 Supplementary Analyses

Two supplementary estimands for the primary endpoint will be estimated:

- 1. The attributes are the same as the primary estimand (Section 1.1) except for the handling of the ICEs. The treatment policy strategy will be applied to handling temporary treatment interruption and intake of prohibited medications having impact on efficacy, while the hypothetical strategy if the participant remained untreated will be applied to premature discontinuation of study treatment.
- 2. The second supplementary estimand will be estimated if the assumption of normality is violated. The attributes are the same as the primary estimand, including the handling of ICEs (See section 1.1), except the variable will be change from baseline in log WASO as measured by PSG at week 4 and the population level summary will be the geometric mean ratio in WASO measured by PSG at Week 4.

4.2.3.1 First Supplementary Analysis

The information about ICEs and strategies to address them for the first supplementary estimand are provided in Table 4-3.

Version 2.0 Page: 23 of 57

Table 4-3: First Supplementary Estimand: ICEs and Strategies to Address Them

ICEs	Proposed Strategy	Data Handling Method	Interpretation
Temporary study treatment interruption ^a	Treatment policy	Utilize the available data regardless of the occurrence of ICE	The treatment effect includes the effect of treatment interruptions
Premature discontinuation of study treatment	Hypothetical	Discard data collected after the ICE	The treatment effect that would be if participants who discontinue the randomized treatment remain untreated on randomized treatment
Intake of prohibited concomitant medication having impact on efficacy	Treatment policy	Utilize the available data regardless of the occurrence of ICE	The treatment effect includes the effect of prohibited concomitant medications impacting sleep

^a Definition of temporary treatment interruption:

Week 4 = Treatment taken <80% during day 1 to the last PSG night at week 4 (inclusive) OR treatment taken on <5 days during the last 7 days up to the last PSG night at week 4 (inclusive).

A treatment policy will be applied to handle the ICE temporary study treatment interruption and intake of prohibited concomitant medication having impact on efficacy. A treatment policy approach for these ICEs is appropriate as this likely reflects the behavior of the target population. According to this strategy, all collected data should be utilized in the analysis irrespective of occurrence of the ICEs.

A hypothetical strategy will be applied to handle the ICE premature discontinuation of study treatment to estimate the treatment effect that would be if participants who prematurely discontinue study treatment remain untreated (i.e., do not receive the experimental study treatment until the planned assessment timepoint). This approach reflects what would happen if participants remained in the study after premature discontinuation of study treatment.

The same MMRM model as the primary estimand (Section 4.2.2) will be used and missing data will be handled in alignment with the first supplementary estimand strategy for ICEs prior to performing the MRMM model.

Although all participants are expected to be followed after ICEs temporary study treatment interruption and intake of prohibited concomitant medication, some missing data may occur. Missing values that occur while the participants continue on their randomized treatment are assumed MAR. Such missing values could be intermittent or monotone and will be imputed using a MCMC MI method.

The washout method (Wang et al. 2003) will be used to impute the unobservable data under the hypothetical scenario for the ICE premature discontinuation of study treatment. A placebo-effect is expected to be seen with the placebo group while the elinzanetant treatment effect will consist of both the placebo-effect and the effect of elinzanetant. The washout method effectively 'washes out' any pre-ICE treatment effect of elinzanetant in participants with an ICE randomized to elinzanetant, while modeling the mean placebo-effect. Missing data in participants randomized to placebo will be assumed MAR.

For participants randomized to elinzanetant, the imputation model will have the dependent variable as the endpoint measurement at week 4 with the baseline measurement and the stratification factor average weekly frequency of moderate-to-severe HFs as independent variables. The imputation model will be estimated only based on placebo participants who

Version 2.0 Page: 24 of 57

remain in the study through week 4 and have available data at week 4. Similarly, week 12 values missing after an ICE will be imputed using the same model specification but with endpoint measurement at week 12 as the dependent variable.

The imputation will be done using a regression model (PROC MI with MONOTONE REG) including covariates described above for each time point and using the MNAR statement to estimate the model from placebo participants only.

To impute missing data for participants randomized to placebo, using MAR assumptions, the imputation will be done using a regression model including measurements from all timepoints before the timepoint being imputed in addition to baseline measurement and the stratification factor (PROC MI with MONOTONE REG). All placebo participants will be included in the imputation model.

PROC MI will be run with the random seed setting SEED=22423 to produce 500 imputed datasets.

Similar analysis steps (i.e., imputation, modeling and combining results) as detailed in Section 4.2.2 will be applied.

